1.3 Schedule of Assessments

					Vi	isit				
				Dou	ıble-Blind T		Period			
					12 v	veeks				Post-
	Screening ^a (Day -21 to Day -1)	Day 0	Week 1 ^b	Week 2	Week 4	Week 6	Week 8	Week 10	End of treatment (Week 12) or ET ^c	treatment Follow-up (21 ± 2 days) ^d
Assessment						± 2 days				
ENTRANCE and HISTORY										
Informed consent	X									
Inclusion and exclusion criteria	X	X								
Confirmation of eligibility	X ^e									
Demography	X									
Medical history	X									
Psychiatric history, including BPD history	X									
Confirm use/no use of ADTs	X									
SCID-5-PD ^f	X									
Diagnostic for concurrent excluded diseases (MINI for Psychotic Disorders)	X									
Prior medication washout ^g	X									
HIV, HBsAg, and anti-HCV	X									
EFFICACY										
ZAN-BPD	X	X	X	X	X	X	X	X	X	
CGI-S		X	X	X	X	X	X	X	X	
CGI-I			X	X	X	X	X	X	X	
PGI-S		X	X	X	X	X	X	X	X	
PGI-C			X	X	X	X	X	X	X	
		X	X	X	X	X	X	X	X	

Table 1.3-1 Sched	ule of Assess	ments									
	Visit										
		Double-Blind Treatment Period									
		12 weeks							1	Post-	
	Screening ^a (Day -21 to	D 0	Week 1 ^b	W. L. 2	W I. 4	Wald	W. J. O.	W1.10	End of treatment (Week 12) or ET ^c	treatment Follow-up $(21 \pm 2$ $days)^d$	
Assessment	Day -1)	Day 0	Week 1	Week 2	Week 4	Week 6 ± 2 days	Week 8	Week 10	OFEI	uays)	
Assessment		X				± 2 days			X		
_		X	X		X	X		X	X		
SAFETY		- 11	21		71	21	I	11	11		
Physical examination ^h	X								X		
Vital signs ⁱ	X	X	X	X	X	X	X	X	X		
Clinical laboratory tests (hematology, serum chemistry, and urinalysis)	x ^j					X			X		
Prolactin (blinded)	X								X		
TSH with reflex to free T ₄ if abnormal	X										
HbA1c	X								X		
ECG^k	X								X		
Urine pregnancy test (FOCBP only) ¹	X	X			X		X		X		
Urine drug screen and blood alcohol test ^m	X					X			X		
C-SSRS ⁿ	X	X	X	X	X	X	X	X	X		
Extrapyramidal symptoms scales (SAS, AIMS, and BARS)		X				X			X		
Adverse events ⁰	X	X	X	X	X	X	X	X	X	X	
Concomitant therapy ^p	X	X	X	X	X	X	X	X	X	X	

Table 1.3-1 Schedu	ıle of Assess	ments								
		Visit								
		Double-Blind Treatment Period								
		12 weeks								
			End of							
	Screeninga								treatment	Follow-up
	(Day -21 to								(Week 12)	(21 ± 2)
	Day -1)	Day 0	Week 1 ^b	Week 2	Week 4	Week 6	Week 8	Week 10	or ET ^c	days) ^d
Assessment						± 2 days				
PHARMACOKINETIC AND PH	IARMACOGI	ENOMIC	SAMPLING	j				T		
Pharmacokinetic sampling ^q						X			X	
		X								
		X								
OTHER PROCEDURES										
IMP dispensing ^S		X^{t}	X	X	X	X	X	X		

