8.7.2 Physical Examination

Physical examinations will be performed at the time points described in the schedule of assessments (Table 1.3-1).

A complete physical examination will consist of measurement of height and waist circumference and a review of the following body systems: head, eyes, ears, nose, and throat; thorax; abdomen; urogenital; extremities; neurological; and skin and mucosa. At screening, height will be measured with a stadiometer, measuring stick or tape. Repeat measurement of height is not required at the physical examinations scheduled for the

Week 12 or ET visit. Waist circumference will be measured at each physical examination (screening and Week 12 or ET), using the provided measuring tape. The following procedures will aid in the standardization of these measurements:

- The subject should be minimally clothed (ie, lightweight clothing; no heavy overgarments).
- Waist circumference should be recorded before a subject's meal and at approximately the same time at each visit.
- Measurement will be accomplished by locating the upper hip bone and the top of the right iliac crest and placing a weighted measuring tape in a horizontal plane around the abdomen at the level of the crest. Before reading the tape measure, the assessor should assure that the tape is snug, but does not compress the skin, and is parallel to the floor. The measurement is to be made at the end of a normal exhalation.³⁸

The investigator (or designee) is responsible for performing the physical examination. If the appointed designee is to perform the physical examination, he or she must be permitted by local regulations and his or her name must be included on the delegation of authority log. Whenever possible, the same individual should perform all physical examinations. Any condition present at the post-treatment physical examination that was not present at the baseline examination should be documented as an AE and followed to a satisfactory conclusion.

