9.2.2 Metabolic Change

In addition to mean change from baseline, incidence of treatment emergent significant changes in fasting lipids, fasting glucose, and metabolic syndrome will be summarized by treatment group using the following criteria.

Criteria for Treatment-Emergent Significant Change in Lipids and Glucose			
LAB PARAMETER	BASELINE ¹	ANYTIME POST BASELINE	
LDL Direct (FAS)ting	Borderline 100-<160	High >=160	
(MG/DL)	Normal/Borderline <160	High >=160	
	Normal <100	Borderline/High >=100	
	Any Value	Increased >=30	
HDL Cholesterol (FAS)ting	Normal >=40	Low <40	
(MG/DL)	Any Value	Decreased >=20	
Triglycerides (FAS)ting	Normal <150	High 200-<500	
(MG/DL)	Borderline 150-<200	High 200-<500	
	Normal/Borderline <200	High 200-<500	
	Normal <150	Borderline/High/Very High >=150	
	Any Value	Increased >=50	
Glucose Fasting, Serum	Normal <100	High >=126	
(MG/DL)	Impaired 100-<126	High >=126	
	Normal/Impaired <126	High >=126	
	Any Value	Increased >=10	

Criteria for Treatment-Emergent Metabolic Syndrome			
DESCRIPTION	ANYTIME POST BASELINE ¹		
Central Obesity	Waist Circumference >=102cm(MALE), >=88cm (FEMALE)		
Dyslipidemia	Triglycerides >= 150mg/dl		
Dyslipidemia	HDL < 40mg/dl (MALE), <50mg/dl (FEMALE)		
Supine Blood Pressure	Systolic>=130mmHg and Diastolic>=85mmHg		
Glucose Fasting, Serum	>=100mg/dl		
Metabolic Syndrome	Met 3 Or More of the Above Criteria at a Visit		

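### SAP 9.2.2: the visible definition of treatment-emergent metabolic syndrome has no baseline condition and no rule for waist circumference at Week 6

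*SAP*

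**What the plan says.** SAP 9.2.2 states that the "incidence of treatment emergent significant changes in fasting lipids, fasting glucose, and metabolic syndrome will be summarized by treatment group". It then prints two tables. The lipid and glucose table pairs a baseline column with a post-baseline column. The second, headed "Criteria for Treatment-Emergent Metabolic Syndrome", has a single time column, "ANYTIME POST BASELINE", with a footnote mark 1.

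The second table lists five criteria: waist ("Waist Circumference >=102cm(MALE), >=88cm (FEMALE"), triglycerides, HDL, supine blood pressure ("Systolic>=130mmHg and Diastolic>=85mmHg") and fasting glucose. A subject has the syndrome if the rule "Met 3 Or More of the Above Criteria at a Visit" is satisfied.

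The components are not all collected at the same visits. Protocol 8.7.2 states: "Waist circumference will be measured at each physical examination (screening and Week 12 or ET". The row "Clinical laboratory tests (hematology, serum chemistry, and urinalysis" in Protocol Table 1.3-1 is marked at screening, Week 6 and Week 12/ET. Vital signs, which include supine blood pressure, are taken at every clinic visit. SAP 9.1 says that safety data are in general analysed as observed case and at last visit. No rule is visible for a visit at which one of the five components was not measured.

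**The concern.** Two features of the definition do not fit its label.

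- **No baseline condition.** Under the visible rule, a subject who met three criteria at screening and still meets them at Week 12 enters the count of treatment-emergent cases. Other emergent outcomes in the SAP do carry a condition: QT/QTc new onset (9.4) requires the value to be absent at baseline, emergent suicidality (9.7) requires none at baseline, and most lipid and glucose rows in 9.2.2 start from a stated baseline category.
- **Two definitions under one name.** At Week 6 only four components exist. A programmer could score waist as not met, carry the screening value forward, or treat Week 6 as not evaluable. Each choice gives a different incidence.

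At stake is how the metabolic safety table can be read. Protocol 2.3 lists increased weight as the most frequent event on the drug in the pooled completed trials (12.1%). A table that mixes existing with new cases is less able to show whether the drug produces new ones.

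**Working it through.** The documents give no figure for metabolic syndrome, so there is nothing to reproduce. They also give no prevalence for any criterion. Every prevalence, correlation and rate below is an assumption.

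**1. Components by visit** (Protocol Table 1.3-1 and 8.7.2)

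| Component | Before dosing | Week 6 | Week 12/ET |
|---|---|---|---|
| Waist | screening | no | yes |
| Triglycerides, HDL, glucose | screening, repeated fasting at Day 0 if screening was non-fasting | yes | yes |
| Supine blood pressure | screening and Day 0 | yes | yes |

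The rule is therefore 3 of 4 at Week 6 and 3 of 5 at Week 12/ET.

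**2. Share of counted cases that are pre-existing.** Let b be the prevalence before dosing, s the probability that such a subject still qualifies after baseline, and n the true new-onset rate. Share = b·s / [b·s + (1 − b)·n].

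- b = 10%, s = 90%, n = 6%: 0.090 / (0.090 + 0.054) = 62.5%. The reported incidence is 14.4%; true new cases are 5.4% of all subjects.
- Lowest over b = 10–30%, s = 70–90%, n = 3–10%: 0.07 / 0.16 = 44%.
- Highest: 0.27 / 0.291 = 93%.

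**3. Effect on the comparison of arms.** Take b = 10%, s = 90%, 120 per arm, and true new onset of 6% on placebo and 12% on drug.

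- Visible rule: 0.09 + 0.9 × 0.06 = 14.4% against 0.09 + 0.9 × 0.12 = 19.8%. Difference 5.4 points, ratio 1.4, z = 0.054 / √(2 × 0.171 × 0.829 / 120) = 1.1.
- With baseline cases removed (120 × 0.9 = 108 per arm): 6% against 12%. Difference 6 points, ratio 2.0, z = 0.06 / √(2 × 0.09 × 0.91 / 108) = 1.5.

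No test is stated for this table; z serves only as a measure of signal to noise.

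**4. Week 6 shortfall, if unmeasured waist is scored as not met.** Share missed = P(waist met and exactly 2 of the other 4) / P(at least 3 of 5).

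For five independent criteria of equal prevalence p this is 6p³(1−p)² / [10p³(1−p)² + 5p⁴(1−p) + p⁵]. At p = 0.20 it is 0.03072 / 0.05792 = 53%. It is 57% at p = 0.10, 44% at 0.40 and 38% at 0.50.

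With unequal prevalences (waist, triglycerides, HDL, blood pressure, glucose) and a common latent correlation:

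| Assumed prevalences (%) | Correlation | At least 3 of 5 | At least 3 of 4, no waist | Missed |
|---|---|---|---|---|
| 35/15/25/5/15 | 0.2 | 7.8% | 2.5% | 68% |
| 35/15/25/5/15 | 0.4 | 10.9% | 4.5% | 59% |
| 50/25/35/10/25 | 0.2 | 18.5% | 7.1% | 62% |
| 50/25/35/10/25 | 0.4 | 21.8% | 10.3% | 53% |
| 60/35/45/15/35 | 0.2 | 31.1% | 14.0% | 55% |
| 60/35/45/15/35 | 0.4 | 33.4% | 18.0% | 46% |

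A wider grid (405 prevalence sets × 7 correlations from 0 to 0.6 = 2,835 cells) gives 22% to 88% missed, above one half in 73% of cells. The proportion of cells above one half drops to 49% at correlation 0.5 and 29% at 0.6.

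**5. Effect on what is reported.** The table counts a subject who qualifies at any post-baseline visit, so a case missed at Week 6 can still be counted at Week 12/ET. I simulated both visits for the six rows above. The between-visit latent correlation was 0.7 to 0.9, and 0% to 20% of subjects had no Week 12/ET visit. The comparator was all five components at both visits.

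- Smallest fall (highest prevalences, correlation 0.4, between-visit 0.9, nobody missing): 41.1% becomes 35.9%, and 1 − 35.9/41.1 = 13%.
- Largest fall (lowest prevalences, correlation 0.2, between-visit 0.7, 20% missing): 11.7% becomes 7.8%, and 1 − 7.8/11.7 = 33%.

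**The case against.** The strongest reply is that footnote 1 sits on the header of the very column in question. Its text was not available for this review and could contain the baseline condition. That stands, and the first half of the point is conditional on it. The same mark is on the baseline header of the lipid and glucose table, which fits a shared definition of baseline at least as well as an exclusion specific to the syndrome, but this does not settle the matter.

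It can also be said that this is one descriptive safety table, and that metabolic effects are examined elsewhere: lipid and glucose shifts in the same section, and weight, weight gain of at least 7% and waist change from screening to Week 12 in SAP 9.5.1. That is correct, and it limits the consequence. It does not make the syndrome table mean what its title says.

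Three stronger readings are tempting and should be resisted.

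- A reader might infer that the rule loses over half of cases. That concerns Week 6 alone, depends on assumed prevalences and on scoring waist as not met (which the SAP does not say), and fails in most cells once the correlation reaches about 0.5. The reported outcome is the anytime incidence.
- A reader might infer that counting existing cases hides any drug effect. Such cases are balanced in expectation by randomisation. They shrink the ratio and add noise, while the risk difference still carries the new cases.
- A reader might infer that requiring both blood pressure limits is a slip. SAP Appendix 1 treats systolic and diastolic values separately, but for a different purpose. Nothing in the documents shows that either limit alone was intended here.

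**Conclusion.** The point holds in limited form. As visible, SAP 9.2.2 labels as treatment-emergent an outcome that has no baseline condition, subject to the text of footnote 1. It also applies a same-visit rule at Week 6, where one of the five components is never scheduled.

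Under the assumed ranges, pre-existing cases make up 44% to 93% of those counted. In the worked example the ratio between arms shrinks from 2.0 to 1.4: diluted, but not lost. The missing Week 6 waist lowers the anytime incidence by about 13% to 33% in relative terms if it is scored as not met; other handling would give other figures, and the SAP leaves the choice open. The primary and key secondary analyses are unaffected.

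**What to change.** Amend SAP 9.2.2 as follows.

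1. Check footnote 1. Unless it already does so, restrict the count and its denominator to subjects who did not meet three or more criteria at baseline. Use the last pre-dose values, in line with the safety baseline in SAP Section 9: screening waist; fasting laboratory values from screening, or from Day 0 if the screening sample was non-fasting; and the last supine blood pressure before the first dose.
2. Score the syndrome at Week 12/ET and at last visit, where all five components are scheduled. If Week 6 is kept, state that screening waist is carried to it.

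The cost is SAP wording and programming, on data that the protocol already collects. The one drawback is a smaller denominator after baseline cases are removed: about 108 instead of 120 per arm if 10% have the syndrome before dosing.

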9.3 Vital Signs

Summary statistics for vital signs will be provided. For the double-blind treatment period vital signs, change from baseline will be summarized for the Safety Sample by treatment group.

Potentially clinically relevant vital signs measurements identified in the double-blind treatment period for the Safety Sample will be summarized by treatment group.

Criteria for identifying vital signs of potential clinical relevance are provided in Appendix 1. All potentially clinically relevant events or changes will be listed and included in summary tables.

9.4 12-Lead ECG

Summary statistics and incidence of potentially clinically relevant changes will be provided for ECG parameters.

For the analysis of QT and QTc, data from three consecutive complexes (representing three consecutive heart beats) will be measured to determine average values. The following QT corrections will be used for reporting purposes in the clinical study report:

- 1) QTcB is the length of the QT interval corrected for heart rate by the Bazett formula: QTcB=QT/(RR)^{0.5} and
- 2) QTcF is the length of the QT interval corrected for heart rate by the Fridericia formula: QTcF=QT/(RR)^{0.33}
- 3) QTcN is the length of the QT interval corrected for heart rate by the FDA Neuropharm Division formula: QTcN=QT/(RR)^{0.37}

Potentially clinically relevant changes in the 12-lead ECG identified in the double-blind treatment period for the Safety Sample will be listed and summarized by treatment group. Criteria for identifying ECG measurements of potential clinical relevance are provided in Appendix 3.

Categorical changes in ECG parameters during the double-blind treatment period will be summarized based on the following criteria:

Categorical Change Criteria in QT/QTc Parameters			
Classification	Category	Criteria	
QT	New Onset (> 450 Msec)	New onset (>450 msec) in QT means a subject who attains a value > 450 msec during treatment period but not at baseline.	
QTc *	New Onset (≥ 450 Msec for men and ≥ 470 Msec for women)	New onset (≥ 450 Msec for men and (≥ 470 Msec for women) in QTc means a subject who attains a value ≥ 450 Msec for men or ≥ 470 Msec for women during treatment period but not at baseline.	
	New Onset (≥ 450 Msec for men and ≥ 470 Msec for women) And > 10% Increase	New onset (≥ 450 Msec for men and ≥ 470 Msec for women) and > 10% increase in QTc means a subject who attains a value ≥ 450 Msec for men or ≥ 470 Msec for women, and > 10% increase during treatment period but not at baseline	

Categorical Change Criteria in QT/QTc Parameters			
Classification Category Criteria		Criteria	
	New Onset (> 500 Msec)	New onset (> 500 msec) in QTc means a subject	
		who attains a value > 500 msec during treatment	
		period but not at baseline.	
	Increase 30 - 60 Msec	Increase from baseline value > 30 and ≤ 60 msec in	
		QTc	
	Increase > 60 Msec	Increase from baseline value > 60 msec in QTc	

^{*} QTc categorical change criteria apply to QTcB, QTcF and QTcN.

9.5 Physical Examinations

By-patient listings will be provided for physical examination.

9.5.1 Body Weight, Waist Circumference and BMI

Analyses of body weight, waist circumference and BMI will be performed for the Safety Sample. The mean change from baseline-to Week 10 (OC) and last visit in the double-blind treatment period in body weight will be tabulated and analyzed using ANCOVA. The ANCOVA models for both the OC and last visit analyses will include the baseline as a covariate and the treatment group as fixed effect. The mean change from screening to Week 12 in waist circumference will be analyzed using ANCOVA.

Percentages of patients showing significant weight gain (≥ 7 % increase in weight), as well as percentages of patients showing significant weight loss (≥ 7 % decrease in weight) from baseline to Week 10 (OC and LOCF) will be analyzed using CMH General Association Test.

[figure not shown]
Body mass index is defined as weight in kilograms divided by the square of height in meters.

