Overall, 9062 subjects received brexpiprazole either alone or coadministered with another marketed medication from the 59 completed brexpiprazole trials conducted under US INDs. Overall, 6403/9062 subjects (70.7%) reported at least 1 treatment-emergent adverse event (TEAE) compared with 1498/2781 subjects (53.9%) who received placebo either alone or coadministered with another marketed medication. The most frequently reported TEAEs (incidence \geq 5% of the total brexpiprazole group and more than total placebo) in all subjects who received brexpiprazole were increased weight (12.1%), headache (9.1%), insomnia (7.8%), akathisia (7.2%), somnolence (6.2%), and dizziness (5.3%). In the total placebo group, headache (8.2%) was the most frequently reported TEAE (incidence \geq 5% of subjects).

Please refer to the IB for a summary of available nonclinical and clinical safety data. 10

[figure not shown]
Trial sites will receive updated versions of the IB, when available, and trial sites should refer to the most current version as needed.

3 Objectives and Endpoints

Table 3-1 Trial Objectives and Endpoints	
Objectives	Endpoints
Primary: To compare the efficacy of brexpiprazole versus placebo for the treatment of subjects with a diagnosis of BPD	in the clinician-administered ZAN-BPD
	Secondary efficacy:
	Change from baseline in the PGI-S for each trial visit during the double-blind treatment period
	PGI-C score
	CGI-I score

- Frequency and severity of AEs
- Changes in ECGs, vital signs, clinical laboratory tests including blinded prolactin, changes in body weight, and physical examinations
- EPS: SAS, the AIMS, and the BARS
- Suicidal ideation and behavior will be assessed using the C-SSRS

Section 9.4 describes the statistical analysis of the endpoints.

4 Trial Design

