4.1 Type/Design of Trial

This will be a 12-week, multicenter, randomized, double-blind, placebo-controlled trial of brexpiprazole in subjects diagnosed with BPD according to the Diagnostic and Statistical Manual of Mental Disorders, 5th edition (DSM-5) and confirmed by a valid diagnostic instrument (Structured Clinical Interview for DSM-5 Personality Disorders [SCID-5-PD]).

The trial will be organized as follows:

Screening Period: The screening period will begin after written informed consent has been obtained and will take place between Day -21 and Day -1 prior to enrollment. Eligible subjects are required to meet all inclusion criteria at both screening and Day 0, including a total score of ≥ 12 on the Zanarini Rating Scale for Borderline Personality Disorder (ZAN-BPD). In addition, a score of ≥ 2 in at least 2 of the following 4 ZAN-BPD subscale items will be required at screening and Day 0: 1) "inappropriate, intense anger or difficulty controlling anger" (hereafter referred to as inappropriate anger), 2) "transient stress-related paranoid ideation or severe dissociative symptoms" (paranoid ideation), 3) "affective instability due to a marked reactivity of mood" (affective instability), and 4) "impulsivity in at least other two areas that are potentially self-damaging" (impulsivity). Following screening, eligible subjects will enter the trial

and be randomly assigned to brexpiprazole 2 to 3 mg/day or placebo in a 1:1 fashion. Randomization will be stratified by site and the status of background antidepressant therapy (ADT) use (with background ADT or without background ADT).

Treatment Period: Subjects will receive their assigned treatment during a 12-week, double-blind treatment period. The primary endpoint and the key secondary endpoint will be the change from baseline in the ZAN-BPD total score and Clinical Global Impression Scale - Severity of Illness (CGI-S) score, respectively. Visits will occur at Day 0 and at the end of Weeks 1, 2, 4, 6, 8, 10, and 12, with phone contact to check on subject status on the weeks the subject does not visit the clinic.

Safety Follow-up: Subjects who do not continue treatment in the open-label extension trial will be followed up for safety reasons via telephone contact or in clinic visit 21 (\pm 2) days after the last dose of investigational medicinal product (IMP). This contact also applies to subjects who are withdrawn prematurely from the trial.

See Figure 1.2-1 for a schematic of the trial.

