3.1 Study Design

This will be a 12-week, multicenter, randomized, double-blind, placebo-controlled trial of brexpiprazole in subjects diagnosed with BPD according to the Diagnostic and Statistical Manual of Mental Disorders, 5th edition (DSM-5) and confirmed by a valid diagnostic instrument (Structured Clinical Interview for DSM-5 Personality Disorders [SCID-5-PD]). See Figure 3.1-1 for a schematic of the trial design.

The trial will be organized as follows:

Screening Period: The screening period will begin after written informed consent has been obtained and will take place between Day -21 and Day -1 prior to enrollment. Eligible subjects are required to meet all inclusion criteria at both screening and the start including a total score of ≥ 12 on the Zanarini Rating Scale for Borderline Personality Disorder (ZAN-BPD). In addition, a score of ≥ 2 in at least 2 of the following 4 ZAN-BPD scale items will be required at screening and Day 0: 1) "inappropriate, intense anger or difficulty controlling anger" (hereafter referred to as inappropriate anger), 2) "transient stress-related paranoid ideation or severe dissociative symptoms" (paranoid ideation), 3) "affective instability due to a marked reactivity of mood" (affective instability), and 4) "impulsivity in at least other two areas that are potentially self-damaging" (impulsivity).

assigned to treatment with brexpiprazole 2 to 3 mg/day or placebo in a 1:1 fashion. Subjects will receive their assigned treatment during an 11-week, double-blind treatment period. The timing of the primary and key secondary endpoints will be blinded to the investigator; these endpoints will be assessed after 9 weeks of assigned treatment (Week 10). Subjects will continue treatment through Week 12 of the trial. The primary endpoint and the key secondary endpoint will be the change from baseline to Week 10 in the clinician administered ZAN-BPD total score and Clinical Global Impression Scale - Severity of Illness (CGI-S) score, respectively. Visits will occur at the end of Weeks 1, 2, 4, 6, 8, 10, and 12/early termination (ET).

[figure not shown]
Post-treatment (Safety) Follow-up Period: Subjects who do not continue treatment in the open-label extension trial will be followed up for safety reasons via telephone contact or in clinic visit 21 (\pm 2) days after the last dose of investigational medicinal product (IMP). This contact also applies to subjects who are withdrawn prematurely from the trial.

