8.1 Primary Efficacy Endpoint

The primary efficacy endpoint is the change from baseline to Week 10 visit in the ZAN-BPD total score.

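### SAP 9.5.1 tests the proportions with at least 7% weight gain or loss only at Week 10, although treatment and weighing run to Week 12 (minor).

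*SAP*

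**What the plan says.** - **Tested proportion.** SAP 9.5.1 defines the comparison as "Percentages of patients showing significant weight gain" (at least 7%), with a matching one for loss, and sets the time point and method: "from baseline to Week 10 (OC and LOCF) will be analyzed using CMH General Association Test".
- **Mean weight.** The same section tests mean change by ANCOVA at Week 10 (OC) and at the last double-blind visit. Waist circumference is analysed to Week 12.
- **Origin of Week 10.** SAP 8.1: "The primary efficacy endpoint is the change from baseline to Week 10 visit in the ZAN-BPD total score". SAP 3.1 explains that the timing of the efficacy endpoints is concealed from the investigator.
- **Treatment after Week 10.** SAP 3.1: "Subjects will receive their assigned treatment during an 11-week, double-blind treatment period"; "these endpoints will be assessed after 9 weeks of assigned treatment (Week 10"); "Subjects will continue treatment through Week 12 of the trial". Protocol 4.1 counts differently: "Subjects will receive their assigned treatment during a 12-week".
- **Weighing.** Protocol Table 1.3-1 schedules vital signs, which include body weight, at every visit up to Week 12/ET.
- **LOCF.** SAP 5.2 fills a missing visit only from an earlier one.
- **Other uses of weight.** SAP 9.3 with Appendix 1 summarizes and lists weight changes of at least 7% over the double-blind period, by arm, with no test stated.
- **General rule.** SAP 9.1 sets observed case and last visit as the default for safety data unless otherwise specified.

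**The concern.** A subject who first reaches a 7% change at Week 12 counts as a non-case in the tested proportion, under OC and under LOCF alike. Nothing in the plan explains this limit. Concealing the endpoint timing protects efficacy ratings, and that reason does not carry over to a reading from a weighing scale. Outside 9.5.1, no analysis in SAP section 9 stops at Week 10: metabolic shifts (9.2.2) use any post-baseline time, and the EPS scales (9.6) use every visit, the last visit and the worst value.

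Weight is also a harm that readers will look for. Protocol 2.3 lists the most frequent TEAEs on brexpiprazole, and the first entry is "increased weight (12.1", in percent. If changes of at least 7% keep appearing late in treatment, the tested comparison leaves out the weeks of longest exposure. The report would then carry a tested Week 10 percentage and an untested whole-period percentage, and the plan does not say how they relate.

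**Working it through.** **1. Time left out.** SAP Table 10.1A gives target day 63 for Week 10 and day 77 for Week 12. (The table names the rating scales, not weight; it is used here only for the timeline.)
- 63/7 = 9 weeks and 77/7 = 11 weeks, which reproduces the two figures in SAP 3.1.
- Left out: 77 − 63 = 14 days = 2 weeks; 14/77 = 18.2%.
- On the protocol's 12-week count the gap is still 2 weeks: 2/12 = 16.7%.

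**2. Can a Week 12 weight enter the test?** OC at Week 10 uses the Week 10 observation. LOCF at Week 10 uses that or an earlier visit. Neither can use Week 12.

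**3. How many cases might this concern?** The documents give no rate of changes of at least 7% and no time course, so every input below is an assumption, with 120 drug-arm subjects and no dropout.

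*Normal model for percent weight change.* P(gain ≥ 7%) = 1 − Φ((7 − m)/s), where m and s are the mean and SD at Week 10. From Week 10 to Week 12, time on treatment grows by a factor of 11/9. Share outside = 1 − P10/P12; extra subjects = 120 × (P12 − P10).

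| m, s at Week 10 | P10 | Growth to Week 12 | P12 | Share outside | Extra per 120 |
|---|---|---|---|---|---|
| 1.5, 3.0 | 3.3% | m×√(11/9), s fixed | 3.8% | 11% | 0.5 |
| | | m×11/9, s fixed | 4.3% | 21% | 1.1 |
| | | m×11/9, s×√(11/9) | 6.0% | 44% | 3.2 |
| 2.0, 3.5 | 7.7% | m×√(11/9), s fixed | 8.6% | 11% | 1.1 |
| | | m×11/9, s fixed | 9.7% | 21% | 2.4 |
| | | m×11/9, s×√(11/9) | 12.0% | 36% | 5.2 |
| 2.5, 3.5 | 9.9% | m×√(11/9), s fixed | 11.3% | 12% | 1.7 |
| | | m×11/9, s fixed | 13.0% | 24% | 3.7 |
| | | m×11/9, s×√(11/9) | 15.4% | 36% | 6.6 |

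*First-crossing model.* Assume 3% to 12% of the drug arm and 1% to 4% of the placebo arm have crossed 7% by Week 10.
- Constant hazard: P12 = 1 − (1 − P10)^(11/9). The drug arm goes from 3–12% to 3.7–14.5%; share outside 17–18%; 0.8 to 3.0 extra subjects.
- Rising hazard (cumulative hazard proportional to time squared): the exponent is (11/9)² = 1.494. The drug arm goes to 4.5–17.4%; share outside 31–33%; 1.7 to 6.5 extra subjects.
- Power of a two-sided 0.05 two-proportion test with 120 per arm: 20–63% at Week 10, 23–71% at Week 12 under constant hazard, 27–79% under rising hazard.

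Across all of these, the share outside runs from about 11% to 44%, and the extra drug-arm cases from about 0.5 to 6.6 per 120.

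**The case against.** The strongest answer is that the weight signal through Week 12 is already covered. The last-visit ANCOVA is a formal test, and for completers the last visit is Week 12. The Appendix 1 summary counts and lists anyone who reaches 7% at any time in the double-blind period, and reported weight increases appear in the TEAE tables. This stands. A reader might infer that late weight gain goes untested or unreported; the documents do not support that. What is absent is a test of the dichotomized outcome that includes Week 12.

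A reader might also infer that well over a third of cases would be missed. That figure needs both the mean and the variance to grow with time; with the SD held fixed, the same starting values give 11% to 24%. Nor do the documents show that weight gain accumulates over these weeks. The 12.1% in Protocol 2.3 is a pooled TEAE incidence from completed trials of differing length, not a rate of gains of at least 7% and not an 11-week rate.

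Three further points are fair:
- The error-control hierarchy in SAP 8.3 covers efficacy only, so no confirmatory claim rests on this p-value.
- A fixed-visit percentage and a whole-period incidence are different quantities, and would differ at Week 12 too. Their disagreement is not itself an error.
- The list of summary tables (SAP section 13) is not in the text available here, so a last-visit or Week 12 table of proportions may be planned there. The point is therefore limited to what 9.5.1 specifies.

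The default in SAP 9.1 does not close the gap, because 9.5.1 specifies otherwise for the proportion. It does show that a last-visit comparison would follow the SAP's own convention.

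**Conclusion.** The point holds as a minor one. The only tested proportion in SAP 9.5.1 omits the last 2 of 11 treatment weeks, with no stated reason and out of line with the rest of SAP section 9. That part follows from the documents alone. Its effect does not: the range of 11% to 44% of Week 12 cases rests on assumed rates and growth models, and if such changes level off before Week 10 the effect could be smaller still. Week 12 weights already reach a tested mean comparison and a descriptive summary, and the primary efficacy result is not affected.

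**What to change.** In SAP 9.5.1:

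1. For the CMH comparisons of gain and loss of at least 7%, add the last visit in the double-blind period and Week 12 (OC). This matches the default in SAP 9.1 and the last-visit analysis of mean weight in the same section.
2. Add Week 12 to the OC weight ANCOVA.
3. Keep Week 10 as an extra row if wanted.
4. Optionally, test the proportion with a change of at least 7% at any post-baseline visit, using the Appendix 1 summary. Label each row, so that fixed-visit percentages and the whole-period incidence are not mistaken for one another.

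The cost is SAP wording and a few table rows. The data are already collected, and efficacy error control is unchanged. The added p-values are nominal and should be labelled so.
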